6.1.2. Laboratory Data

Laboratory data will be listed and summarized by treatment in accordance with CaPS. Baseline is as defined in Section [3.5.2](#).

6.1.3. Vital Signs

Absolute values and changes from baseline in supine systolic and diastolic blood pressure and pulse rate will be summarized by treatment and visits, according to CaPS. Tables will be paged by parameter. Baseline is as defined in Section [3.5.3](#).

Maximum and minimum absolute values and changes from baseline for vital signs will also be summarized by treatment using categories as defined in Appendix 1. Numbers and percentages of participants meeting the categorical criteria will be provided. All planned and unplanned postdose timepoints will be counted in these categorical summaries. All values meeting the criteria of potential clinical concern will be listed.

If necessary, maximum increases or decreases in vital signs may be summarized in addition to the above.

[figure not shown]

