1.3. Schedule of Activities

The SoA table provides an overview of the protocol visits and procedures. Refer to the **STUDY ASSESSMENTS AND PROCEDURES** section of the protocol for detailed information on each procedure and assessment required for compliance with the protocol.

The investigator may schedule visits (unplanned visits) in addition to those listed in the SoA table, in order to conduct evaluations or assessments required to protect the well-being of the participant.

Visit Identifier ^a Abbreviations used in this table may be found in Appendix 8 .	Screening	CRU Confinement							Follow-Up							ET	
		-28 to -2	-1	1	2	3	4	5	8	15	29	43	57	71	99	127	157
Days Relative to Day 1	-28 to -2	-1															
Visit Window (days)	-	-	-	-	-	-	-	-	±1	±3	±3	±3	±3	±3	±3	±3	-
Hours After Dose			0 ^b	1	2	6	12	24	48	72	96	-	-	-	-	-	-
Informed consent	X																
Demography	X																
CRU confinement		X	→	→	→	→	→	→	→	→	X						
Visit to the CRU	X	X										X	X	X	X	X	X
Inclusion/exclusion criteria	X	X															
Medical/medication history (update)	X	X															
History of illegal drug & alcohol and tobacco use	X	X															
Report prior or concomitant treatments	X	X	→	→	→	→	→	→	→	→	X	X	X	X	X	X	X
Contraception check	X	X									X	X	X	X	X	X	X
Physical exam (including height & body weight at screening, only) ^c	X	X															X
Single 12-Lead ECG	X		X								X		X		X	X	X
Supine BP, PR and oral or axillary temperature	X		X								X		X		X	X	X
Chest X-ray ^d	X																
Serious and nonserious AE monitoring	X	→	→	→	→	→	→	→	→	X	X	X	X	X	X	X	X
Study intervention administration			X ^e														
Safety laboratory (after ≥4 hour fasting) including PT, INR, aPTT	X	X					X			X	X	X	X	X	X	X	X
Viral surveillance (CMV, VZV, EBV, HHV6, HSV-1/2)	X									X	X	X		X		X	X

Visit Identifier ^a Abbreviations used in this table may be found in Appendix 8 .	Screening	CRU Confinement								Follow-Up								ET
		-28 to -2	-1	1		2	3	4	5	8	15	29	43	57	71	99	127	157
Days Relative to Day 1	-28 to -2	-1	1		2	3	4	5	8	15	29	43	57	71	99	127	157	-
Visit Window (days)	-	-	-		-	-	-	-	±1	±3	±3	±3	±3	±3	±3	±3	±3	-
Hours After Dose			0 ^b	1	2	6	12	24	48	72	96	-	-	-	-	-	-	-
FSH in females amenorrheic ≥12 months, only	X																	
Pregnancy test (WOCBP only)	X	X									X		X		X	X	X	X
HIV, HBsAg, HBsAb, HBCab, HCVAb, syphilis	X																	
HBV DNA, if applicable ^f	X															X		X X
Interferon Gamma Release Assay ^g	X																	

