6.1.1.1. Intravenous Infusion Discontinuation

- If a participant experiences symptoms typical of an allergic reaction, the study intervention infusion should be discontinued immediately and permanently.
- If a participant experiences symptoms typical of IRR (eg, lightheadedness, nausea, chills, fever), the study intervention infusion should be stopped. At the discretion of the investigator, the infusion can be restarted at a slower rate if symptoms are resolved within 1 hour after the stop of infusion. If symptoms return, then the study intervention infusion should be discontinued immediately and permanently.
- In the event that there is an infusion interruption, the entire duration of study intervention infusion, from the initial start of infusion to the completion of infusion, should not exceed 3 hours. Participants will receive appropriate treatment at the discretion of the investigator.

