8.2.3.1. Temperature

Temperature (oral or axillary) will be measured. No eating, drinking, or smoking is allowed for 15 minutes prior to the measurement.

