9.3.4. Other Safety Analyses

AEs, ECGs, BP, PR and safety laboratory data will be reviewed and summarized on an ongoing basis during the study to evaluate the safety of participants. Any clinical laboratory, ECG, BP, and PR abnormalities of potential clinical concern will be described. Safety data will be presented in tabular and/or graphical format and summarized descriptively, where appropriate.

Medical history and physical examination and neurological examination information, as applicable, collected during the course of the study will be considered source data and will not be required to be reported, unless otherwise noted. However, any untoward findings identified on physical and/or neurological examinations conducted during the active collection period will be captured as AEs, if those findings meet the definition of an AE. Data collected at screening that are used for inclusion/exclusion criteria, such as laboratory data, ECGs, and vital signs, will be considered source data, and will not be required to be reported, unless otherwise noted. Demographic data collected at screening will be reported.

CCI

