3. ENDPOINTS AND BASELINE VARIABLES: DEFINITIONS AND CONVENTIONS

3.1. Primary Endpoint(s)

Primary endpoints are assessments of AEs/SAEs including IRR, infusion sites and viral infections, vital signs, ECGs and laboratory tests.

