3.5.3. Vital Signs

Supine systolic and diastolic blood pressure and pulse rate (PR) will be taken at all time points listed in the Schedule of Activities given in the protocol. The last pre-dose measurement at Day 1 will be used as the baseline.

The maximum decrease and increase from baseline over all measurements taken postdose for supine systolic and diastolic blood pressures will be determined. The maximum increase from baseline will be calculated by first subtracting the baseline value from each postdose measurement to give the change from baseline. The maximum of these values over the entire study will then be selected, except in the case where a participant does not show an increase. In such an instance, the minimum decrease should be taken. Similarly, the maximum decrease from baseline will be determined by selecting the minimum value of the change from baseline. In cases where a subject does not show a decrease, the minimum increase should be taken.

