8. APPENDICES

Appendix 1. Categorical Classes for Vital Signs and ECG of Potential Clinical Concern

Categories for Vital Signs

Systolic BP (mm Hg)	min. <90	
Diastolic BP (mm Hg)	min. <50	
Pulse rate (bpm)	min. <40	max. >120
Systolic BP (mm Hg) change from baseline	max. increase ≥ 30	max. decrease ≥ 30
Diastolic BP (mm Hg) change from baseline	max. increase ≥ 20	max. decrease ≥ 20

Categories for PR and QRS

PR (ms)	max. ≥ 300
QRS (ms)	max. ≥ 140
PR (ms) increase from baseline	Baseline >200 and max. $\geq 25\%$ increase or Baseline ≤ 200 and max. $\geq 50\%$ increase
QRS (ms) increase from baseline	$\geq 50\%$ increase

Categories for QT

[figure not shown]
Absolute value	≥ 500
----------------	------------

Categories for QTcF

Degree of Prolongation	Mild (msec)	Moderate (msec)	Severe (msec)
Absolute value	≥ 450 and <480	≥ 480 and <500	≥ 500
Increase from baseline		≥ 30 and <60	≥ 60

Measurements that fulfill these criteria are to be listed in report.

PFIZER GENERAL BUSINESS

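### Does the SAP need its own written analysis of body temperature, given that vital signs are a primary endpoint?

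*SAP*

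**What the plan says.** SAP 3.1 defines the endpoint broadly: "Primary endpoints are assessments of AEs/SAEs including IRR, infusion sites and viral infections, vital signs, ECGs and laboratory tests". It does not say which vital signs are meant.

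The protocol counts temperature as one of them. Its Schedule of Activities has a single row for "Supine BP, PR and oral or axillary temperature", separate from the COVID-19 temperature check. Section 8.2.3.1, which sits under 8.2.3 Vital Signs, states: "Temperature (oral or axillary) will be measured".

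The specific SAP text is narrower. Section 3.5.3 says: "Supine systolic and diastolic blood pressure and pulse rate (PR) will be taken at all time points listed in the Schedule of Activities". It then sets the last Day 1 pre-dose value as baseline. Section 6.1.3 says: "Absolute values and changes from baseline in supine systolic and diastolic blood pressure and pulse rate will be summarized by treatment and visits". Appendix 1, headed "Categorical Classes for Vital Signs and ECG of Potential Clinical Concern", has five vital-sign rows: systolic pressure, diastolic pressure, pulse, systolic change and diastolic change.

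The protocol's own safety-analysis text has the same narrow scope. Section 9.3.4 says: "AEs, ECGs, BP, PR and safety laboratory data will be reviewed and summarized on an ongoing basis during the study".

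**The concern.** A component of the primary endpoint is measured on a schedule, yet the SAP neither says how it is analysed nor says that it is left out. A reader could conclude that the temperature readings will be collected and never reported.

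Temperature also bears on the risks that the protocol names. Section 6.1.1.1 of the protocol gives fever as one of four examples of "symptoms typical of IRR (eg, lightheadedness, nausea, chills, fever". Viral infection is a potential risk in section 2.3, and both infusion reactions and viral infections are named in the primary endpoint. If temperature appears only when somebody reports a fever as an adverse event, smaller or unreported rises would not be seen by treatment group. That lost information is what is at stake. In a purely descriptive plan no estimate is biased.

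**Working it through.** No figure in the plan needs to be reproduced. The check is to compare what the protocol schedules with what the SAP's rules, specific and general, provide.

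**Step 1: count the parameters.** Scheduled: systolic pressure, diastolic pressure, pulse and temperature, which is 4. Named in SAP 3.5.3 and 6.1.3: the first three. Not named: 4 − 3 = 1.

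**Step 2: see what the rest of the SAP supplies for the unnamed one.**

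| Element | Blood pressure and pulse | Temperature |
|---|---|---|
| Baseline | SAP 3.5.3, Day 1 pre-dose | The 3.5.3 baseline sentence stands under Vital Signs and is not worded as limited to pressure and pulse. Failing that, SAP 3.4 gives a default: Day 1 before dosing, or the last earlier value |
| Grouping | SAP 6.1.3, by treatment and visit | SAP 5.2: all data by treatment (300 mg, 900 mg, pooled placebo) |
| Statistics | CaPS, with SAP 5.2.2 as default | SAP 5.2.2: count, mean, SD, median and range for continuous endpoints |
| Listing | SAP 6.1, per CaPS | SAP 6.1, per CaPS, as part of the primary endpoint |
| Extremes | SAP 6.1.3 and Appendix 1 | The last sentence of SAP 6.1.3 allows maximum rises or falls in vital signs to be summarised if needed |
| Category | Appendix 1 | None |

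Every row but the last has a workable default. The general rules do not name temperature, but neither do they exclude it.

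**Step 3: ask whether the missing category is an inconsistency.** Appendix 1 does not aim to cover every parameter. ECG heart rate is summarised by visit in SAP 6.1.4 but has no category. Pulse has limits on the value but none on the change. Blood pressure has a lower limit on the value but no upper one. The documents give no numerical fever threshold from which a temperature row could be built. The lack of one is therefore in keeping with the rest of the appendix.

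**Step 4: follow a meaningful temperature rise through the plan.** Protocol Appendix 3 makes an abnormal vital sign an adverse event when the investigator considers it clinically significant, so it enters the AE tables. If blinded medical review judges it potentially infusion-related, it also enters the separate infusion-reaction tables of SAP 6.1.1. Viral infections have their own tables in the same section, and protocol 8.2.8 adds blood sampling for six named viruses.

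**Step 5: ask what an extra panel could show.** By Table 2 of the SAP the groups are 5 on 300 mg, 5 on 900 mg and 1 + 1 = 2 on pooled placebo. Mean changes against two placebo participants would not separate a small drug effect from ordinary variation. Individual listings carry most of the information at this size, and SAP 6.1 already calls for listings.

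I have not counted scheduled readings. The Schedule of Activities row has lost cells in the text available to me, so its marks cannot be placed safely. For the same reason I do not say whether any scheduled reading falls close to the infusion.

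**The case for a change.** The strongest case for a change is that explicit lists tend to override general rules. Sections 3.5.3 and 6.1.3 name three parameters, and a programmer working from them could reasonably build three panels and stop. SAP version 2 revised the infusion-reaction and viral-infection definitions and specified the vital-sign categories, yet temperature is still unmentioned. The earlier study in healthy participants (protocol 2.2.2.1) saw an apparently higher rate of mild upper respiratory infection on active drug, so temperature is clinically relevant. Nor does the rule in protocol 8.2.9 that treats COVID-19 assessments as source data remove the temperature scheduled with the vital signs.

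Much of this stands. The omission is real, the COVID-19 rule does not explain it, and two analysts could differ on whether to print a by-visit temperature table. CaPS would probably settle that, but it is not in the documents.

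The step from there to a needed change does not stand. No stated rule gives a wrong result for temperature. The agreement between SAP 6.1.3 and protocol 9.3.4 suggests that pressure and pulse may be the intended scope of the detailed tables. The risks that make temperature interesting are followed more directly by AE review and viral sampling than a table of mean temperatures would follow them.

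**Conclusion.** The SAP does not name temperature, and that is the whole of the gap: one of four vital-sign parameters, in a descriptive study of 12 participants. Its general rules cover baseline, grouping, statistics and listing, and clinically significant fever is reported through adverse events. No estimate, error rate or conclusion changes whether temperature is tabulated, listed only or left to the AE data. Analysts can fill this sensibly when they lay out the vital-signs tables, so the plan need not be changed.

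This rests on two assumptions. The first is that the general wording of SAP 3.4, 5.2 and 6.1 is read to include a scheduled primary-endpoint measurement. The second is that CaPS, which I could not see, contains nothing that would suppress temperature from the listings. If the second failed, the loss would still be of descriptive detail only.

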6.1.4. Electrocardiograms

Absolute values and changes from baseline for the ECG parameters (QT interval, heart rate, QTcF interval, PR interval, and QRS interval) will be summarized by treatment and visits following the CaPS. Tables will be paged by parameter. Baseline is as defined in Section [3.5.4](#).

Maximum increase from baseline for QTcF interval, PR and QRS over all measurements will be summarized by treatment group, according to CaPS.

ECG endpoints and changes from baseline (QTcF, PR and QRS) will also be summarized by cohort and treatment using categories as defined in Appendix 1. The number (%) of

PFIZER GENERAL BUSINESS

participants meeting the categorical criteria will be provided. All planned and unplanned postdose timepoints will be counted in these categorical summaries. All values meeting the criteria of potential clinical concern will be listed.

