9.3.1. General Considerations

All analyses described below will be conducted by treatment. In addition, data from placebo in Cohort 1 and Cohort 2 will be pooled.

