9.3.2.1. Electrocardiogram (ECG) Analysis

Changes from baseline for the ECG parameters (QT interval, HR, QTc interval, PR interval, and QRS interval) will be summarized by treatment and time.

The number (%) of participants with maximum postdose QTc values and maximum increases from baseline in the following categories will be tabulated by treatment:

Safety QTc Assessment

Degree of Prolongation	Mild (msec)	Moderate (msec)	Severe (msec)
Absolute value	>450-480	>480-500	>500
Increase from baseline		30-60	>60

In addition, the number of participants with corrected and uncorrected QT values ≥ 500 msec will be summarized.

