1. VERSION HISTORY

Table 1. Summary of Changes

Version/ Date	Associated Protocol Amendment	Rationale	Specific Changes
1 21JUL2021	Original 26MAY2021 Amendment 1 09JUL2021	N/A	N/A
2 14APR2022	N/A	Some clarifications were added.	Section 6.1.1: Added clarification on the definition of IRR and viral infections. Sections 6.1.3 and 6.1.4: The categorical classes for vital signs and ECGs were specified in Appendix 1. Overall: Minor edits for the description maintenance.

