5.2. General Methods

All data will be descriptively summarized by treatment (PF-06823859 300 mg, PF-06823859 900 mg, and placebo). Data from placebo in Cohort 1 and Cohort 2 will be pooled for all analyses.

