6. ANALYSES AND SUMMARIES

6.1. Primary Endpoint(s)

[figure not shown]
The primary endpoints will be listed and summarized by treatment (PF-06823859 300 mg, PF-06823859 900 mg, and placebo) in accordance with CaPS, where the resulting data presentations will consist of participants from the safety analysis set. Data from placebo in Cohort 1 and Cohort 2 will be pooled.

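### Does the cohort split in the categorical ECG summary (SAP 6.1.4) break the pooled-placebo rule in a way that needs correcting?

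*SAP*

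**What the plan says.** The general rules are consistent. Protocol 9.3.1 states: "All analyses described below will be conducted by treatment", and adds that placebo is combined over the two cohorts. SAP 5.2 names three groups (300 mg, 900 mg, placebo) and states: "Data from placebo in Cohort 1 and Cohort 2 will be pooled for all analyses". SAP 6.1, the parent section for the primary endpoints and so for ECGs, repeats: "Data from placebo in Cohort 1 and Cohort 2 will be pooled".

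The specific rules agree, with one exception. For the QTc classes, protocol 9.3.2.1 says that "maximum postdose QTc values and maximum increases from baseline in the following categories will be tabulated by treatment". For vital signs, SAP 6.1.3 says that "changes from baseline for vital signs will also be summarized by treatment using categories as defined in Appendix 1". The first two paragraphs of SAP 6.1.4 are also by treatment. Its third paragraph, on the categorical ECG results, instead says that they "will also be summarized by cohort and treatment using categories as defined in Appendix 1".

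The class boundaries also differ. Protocol 9.3.2.1 uses >450-480, >480-500 and >500 ms for the absolute value, and 30-60 and >60 ms for the increase. SAP Appendix 1 closes each class at its lower end: from 450 to below 480, from 480 to below 500, and 500 or more; for the increase, from 30 to below 60, and 60 or more. The SAP's version history records for version 2: "The categorical classes for vital signs and ECGs were specified in Appendix 1".

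**The concern.** ECGs are part of the primary endpoint. Read literally, the SAP gives the programmer two layouts for the same summary, and it has no formal clause saying which prevails. Following 6.1.4 would give the categorical ECG results a different placebo layout from the other safety summaries, with columns in which a percentage describes one person.

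Two further points seemed to add weight. The QTc boundaries move between the protocol and the SAP, and the version history does not say that they depart from the protocol. In addition, the sentence in 6.1.4 names QTcF, PR and QRS in brackets but not QT, although protocol 9.3.2.1 asks for "the number of participants with corrected and uncorrected QT values" of 500 ms or more. If that count were lost, a request in the protocol would go unmet.

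**Working it through.** **Column sizes.** Inputs are the randomization scheme (protocol Table 1, SAP Table 2): Cohort 1 has 5 on 300 mg and 1 on placebo; Cohort 2 has 5 on 900 mg and 1 on placebo. The total is 2 × (5 + 1) = 12, which reproduces the figure in protocol 9.5 (10 active, 2 placebo).

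| Layout | 300 mg | 900 mg | Placebo |
|---|---|---|---|
| By treatment, placebo pooled | 5 | 5 | 1 + 1 = 2 |
| By cohort and treatment | 5 | 5 | 1 and 1 |

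Dose and cohort coincide, so splitting by cohort cannot divide an active group. The active percentages move in steps of 1/5 = 20% under both layouts.

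**Placebo percentages.** Pooled, k/2 for k = 0, 1, 2 gives 0, 50 or 100%. Split, k/1 for k = 0, 1 gives 0 or 100% in each column. Adding the two split counts recovers the pooled result: (0, 0) gives 0%, (0, 1) or (1, 0) gives 50%, and (1, 1) gives 100%. The split therefore loses nothing.

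**Which rule an analyst would apply.** SAP 5.2.1 to 5.2.3 each allow for exceptions specified elsewhere. The pooling sentence in 5.2 allows none and covers every analysis. Section 6.1 then repeats it for this endpoint. With placebo pooled first, adding cohort does no more than label the two active columns.

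**Class boundaries.** Comparing the two sets at whole milliseconds from 350 to 600 (absolute) and from -60 to +120 (increase):

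| Value (ms) | Protocol class | SAP class |
|---|---|---|
| 450 | none | mild |
| 480 | mild | moderate |
| 500 | moderate | severe |
| +60 | moderate | severe |

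All other values agree, including +30, which is moderate in both. At each of the four differing values the SAP assigns the higher class, so it cannot under-report relative to the protocol.

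**QT of 500 ms or more.** The bracket in 6.1.4 can be read as qualifying only the changes from baseline. Appendix 1 fits that reading: QTcF, PR and QRS have rows for an increase, while QT has only an absolute row, at 500 ms or more. QT is among the ECG parameters named in the first paragraph of 6.1.4, and the sentence refers to the Appendix 1 categories. Both counts that the protocol requests therefore have a row: QT at 500 or more, and the severe QTcF class at 500 or more.

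**The case for a change.** The best case for an edit is that the conflict lies inside the SAP. The protocol's permission for the SAP to modify it therefore does not settle the matter. No section gives a reason for a cohort split, the vital-signs summary built on the same appendix has none, and deleting two words would cost nothing. The version history does list the Appendix 1 classes among its specific changes, but presents them as clarification and does not say that they differ from the protocol.

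These facts stand. What does not stand is the step from an untidy phrase to a problem in the analysis. The lack of any reason for a split, and its absence from the sister summary, are also what show an analyst that the phrase is stray. The missing precedence clause matters little when the pooling rule is stated twice without exception. On the boundaries, both documents require an amendment only for major changes to the primary endpoint or its analysis. Moving the equality sign at four values, always towards the higher class, is hard to call major.

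**Conclusion.** The inconsistency is genuine but clerical, and correcting it would bring no analytic gain. At most, two placebo participants appear in two columns of one instead of one column of two. The active columns, the other ECG summaries and the individual listings stay the same. The boundary difference matters only if a maximum QTc or its increase falls exactly on one of four values, and then the SAP is the stricter set. The apparent QT omission does not hold on a natural reading of 6.1.4 with Appendix 1.

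This rests on three assumptions: enrolment follows the planned 5:1 scheme in each cohort (replacements could shift the counts slightly); no participant receives the other cohort's dose; and the results remain descriptive, as protocol 9.1 and 9.5 state. If the SAP is reopened for another reason, the phrase can be tidied then.
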